3.1.1 Summary statistics specific to PK data

For CZP Plasma concentrations, geometric mean, geometric coefficient of variation (geometric CV (%)), 95% CI for the geometric mean (assuming log-normally distributed data) will only be calculated if at least $\frac{2}{3}$ of the values of interest are above the LLOQ (0.032 ug/mL). If this is not the case, only median, minimum and maximum will be presented.

The 95% CI for the geometric mean will be calculated by obtaining the lower and upper 95% CI for the arithmetic mean on the log-transformed data and back-transforming to obtain the respective values for the geometric CI.

The geometric CV (%) will be calculated using the following formula:

$$CV = \sqrt{e^{SD_{ln}^2} - 1}$$

where SD_{ln} represents the standard deviation of the log-transformed plasma concentration values.

The intraclass correlation coefficient (ICC) will be calculated using the following formula:

$$\rho = \frac{\sigma_r^2}{\sigma_r^2 + \sigma_\epsilon^2}$$

Where σ_r^2 represents the variance of the random effect and σ_ϵ^2 represents the variance of the residual in the linear mixed effects model as described in Section 9.1.2.

3.1.2 Unit conversion for height, weight and BMI formula

Even if BMI is available in the database, BMI (in kg/m²) will be recalculated during analysis based on height (in m) and weight (in kg) values collected in the database, and the calculated values will be used in the statistical analysis.

If height is recorded in inches, the height conversion is:

$$\text{Height (m)} = 0.0254 * \text{Height (inches)}$$

If weight is recorded in pounds, the weight conversion is:

$$\text{Weight (kg)} = 0.45359237 * \text{Weight(lb)}$$

The formula for BMI (kg/m²) calculation is:

$$\text{BMI} = \frac{\text{Weight (kg)}}{(\text{Height (m)})^2}$$

3.2 General study level definitions

3.2.1 Analysis time points

3.2.1.1 Relative day

The relative day will be included in some listings and will be calculated as described below. The way that relative day is calculated depends on when the given event occurs relative to the date of first day of enrolment into the study.

Relative day 1 is the date of first day of enrolment into the study.

- If the study participant is not discontinued from the study and the event start (stop) date occurred on or after the first day of enrolment into the study, but prior to the SFU visit date, relative day is calculated as start (stop) date of the event minus date of first day of enrolment into the study + 1.
- If the study participant is discontinued from the study and the event start (stop) date occurred on or after the first day of enrolment into the study, but prior to the stop date, relative day is calculated as start (stop) date of the event minus date of first day of enrolment into the study + 1.
- If the study participant completes the SFU visit and the event start (stop) date occurred after the SFU visit date, the relative day to the most recent CZP dose is calculated as start (stop) date of the event minus most recent CZP dose date. The relative day in this situation should be preceded by a ‘+’

- If the study participant does not complete the SFU visit and the event start (stop) date occurred after the study stop date, the relative day to the most recent CZP dose is calculated as start (stop) date of the event minus most recent CZP dose date. The relative day in this situation should be preceded by a ‘+’
- If the event start (stop) date occurred before the first day of enrolment into the study, the relative day is calculated as start (stop) date of the event minus first day of enrolment into the study. The relative day in this situation should be preceded by a ‘-’.

Relative day will only be computed for fully completed dates and will be left blank for partial dates.

3.2.2 Study periods

The study consists of a Screening Period, Sampling Period (consisting of a Pregnancy Period and Postpartum Period), and a Safety Follow-up (SFU) contact, as described below. Gestational week (i.e., week of gestational age) is determined from the time since the first day of the last menstrual period or, if the participant had undergone in vitro fertilization (IVF), from the date of birth and gestational age recorded for the pregnancy outcome and then back-calculated to get the gestational week for each PK sample.

- Screening Period: Starts at the confirmation of pregnancy at screening and ends at the start of the enrolment date (Participant having taken CZP for at least 12 weeks at the same dosing regimen prior to the Enrollment Visit, which must take place at ≤ 10 weeks gestational age).
- Sampling Period: The total study duration for a study participant will be a maximum of 53 weeks (40 weeks gestation period and up to 13 weeks (± 3 days) postpartum).
 - Pregnancy Period: Starts at enrolment and ends on the day of delivery. Pregnancy may take the entire length of the gestation period (up to 40 weeks).
 - Postpartum Period: Starts the day after the date of delivery and ends after the final postpartum sample is taken.
 - Trimesters: Defined using the gestational week and distinguished as first (up to 12 weeks and 6 days’ gestation), second (13–28 weeks and 6 days’ gestation), and third (any time at or after 29 weeks’ gestation)
- Safety Follow-up contact: The SFU visit will be defined for all study participants who complete the study, or for study participants who discontinue early including those who discontinue from CZP. For participants who complete the study, the SFU will be conducted 5 weeks (± 5 days) after final study visit. For participants who discontinue, the SFU visit will still be completed.

In case that the SFU date is not available, the last contact date will be used as end of the SFU period. A participant is considered to have completed the study if she has completed all phases of the study per protocol including the final study contact (SFU).

The end of the study is defined as the date of the SFU/last contact of the last participant in the study.

3.3 Definition of Baseline values

For summaries of all participant demographic data, Baseline value for a study participant is defined as the latest measurement for that study participant up to and including the day of enrolment into the study, unless otherwise stated. If a Baseline assessment is taken on the same day as study enrolment, it is eligible to be used as the Baseline value, even in the case that the time of the assessment is recorded as taking place after the time of study enrolment. However, such cases should be rare as study center personnel are instructed to do all assessments at the Baseline visit prior to enrolment. If a Baseline measurement is missing or not collected, and a Screening value is available, the Screening value will be utilized as Baseline instead. If no measurement is available prior to study enrolment, then the Baseline value is treated as missing.

For summaries of CRP, Albumin, BMI and anti-CZP antibody data, the postpartum measurement will be used as the reference point based on the postpartum measurement collected at Visit 5. If there was no sample collected at Visit 5, then the last available postpartum sample will be used. If the postpartum measurement is missing or not collected (i.e., the postpartum value is not available), then the reference value is treated as missing.

For summaries of plasma concentration, the postpartum measurements will be used as the reference point instead of the day of enrolment based on both the predose and postdose postpartum PK samples. If either the predose or postdose postpartum PK measurement is missing or not collected, (i.e., the postpartum value is not available), then the respective reference value is treated as missing.

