2.1.2 Secondary objectives

- To assess the formation of anti-CZP antibodies (ADA) across the course of pregnancy
- To assess the safety of CZP in study participants with chronic inflammatory diseases across the course of pregnancy

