2.2.1.1 Secondary Outcome variables

- Plasma levels of ADA throughout the study period
- Treatment-emergent adverse events from time of informed consent through Safety Follow-up (SFU)
- Pregnancy outcome

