9.2.1 Anti-drug antibodies sample status category definitions

Anti-drug antibodies (ADA) will be measured using a three-tiered assay approach: screening, confirmatory and titration assay.

Samples will first be evaluated in the screening assay (reported as ‘negative screen’ or ‘positive screen’), followed by analysis of screened positive samples in the confirmatory assay to confirm the true positivity of the samples (reported as ‘negative immuno-depletion’ or ‘positive immuno-depletion’). Samples that are confirmed as positive in the confirmatory assay will be evaluated in a titration assay to quantify the ADA level and will be reported as titer (reciprocal dilution factor including minimum required dilution [MRD]).

The ADA sample status will be determined for each visit where samples were collected for ADA analysis (both scheduled and any unscheduled visits).

- Sample values that are either ‘negative screen’ or the combination of ‘positive screen’ and ‘negative immuno-depletion’ will be defined as **ADA negative** if corresponding CZP concentrations are equal or below the validated drug tolerance limit of the ADA assay (100 ug/mL CZP) allowing detection of 100ng/mL ADA.

- Sample values that are either ‘negative screen’ or the combination of ‘positive screen’ and ‘negative immunodepletion’ but with corresponding CZP concentrations above the validated drug tolerance limit of the ADA assay will be defined as **ADA inconclusive**.
- Sample values that are ‘positive screen’ and ‘positive immunodepletion’ will be defined as **ADA positive**.
- Samples that could not be tested for ADA status due to inadequate sample volume, mishandling, or errors in sample collection, processing, storage, etc., will be defined as **Missing**.

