9.2.2 Anti-drug antibodies participant titer classification

Once determined positive, a study participant’s highest titer will be used to categorize (“titer classification”) the study participant as follows:

- Positive ≤ 32
- Positive $>32 - \leq 128$
- Positive $>128 - \leq 512$
- Positive $>512 - \leq 1024$
- Positive $>1024 - \leq 4096$
- Positive >4096

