9.2.3 ADA titer and classification summaries and analyses

The fold difference increase from postpartum value, i.e., the minimum significant ratio (MSR) determined during assay validation, will be reported in the relevant tables, listings and figures. It reflects the fold difference in titer level that is considered higher than the assay variation in titer determination.

The following summaries, figures and listings will be produced using the MSR and will be presented using the SS:

- Summary table displaying the number and percentage of study participants with a positive ADA, negative ADA, inconclusive or missing ADA sample status at the time of each visit by dosing regimen.
- Spaghetti plots of the individual time course plots of ADA titer (y-axis) by time (x-axis) for participants with at least one ADA positive sample status, with one line representing one study participant. Separate plots will be presented for each dosing regimen. Plots may be presented using a semi-logarithmic scale for the ADA titers (ADA negative samples will therefore be excluded from the plot). Time will be presented using gestational week.
- Summary statistics of ADA titers (mean, min, max, geomean) per time point and dosing regimen.
- Summary of titer classification for all study participants who test positive at any visit will be presented by category.
- The ADA results will be listed including the results from the screening assay, confirmatory assay, and titration assay (titer level), the ADA sample status, the drug concentration with indication if the drug level exceeds the ADA assay tolerance for detecting 100 ng/ml ADA or alternative level as defined above (Y/N).

In addition, the following figures will be produced to illustrate the impact of ADA on PK:

- Spaghetti plots of the individual CZP plasma concentrations (each participant corresponding to a line) over time will be produced on a linear and semi-logarithmic scale according to ADA titer classification. Gestational week should be indicated below the x-axis.
- Time course plots of individual CZP plasma concentrations (one plot per participant) superimposed with the participant's corresponding ADA titer over the course of the study will be presented. Plots may be presented using a semi-logarithmic scale for the ADA titers (ADA negative samples will therefore be excluded from the plot). Time will be presented using gestational week.

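### The ADA fold increase is referenced to the postpartum value although the objective is ADA formation, and no planned table separates ADA present at enrolment from ADA newly formed or boosted later

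*SAP*

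**What the plan says.** The secondary objective in SAP 2.1.2 is "To assess the formation of anti-CZP antibodies (ADA) across the course of pregnancy". The matching variable in SAP 2.2.1.1 is "Plasma levels of ADA throughout the study period". Unlike the PK variable in SAP 2.2.1, it contains no comparison with postpartum.

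SAP 3.3 then sets the reference: "For summaries of CRP, Albumin, BMI and anti-CZP antibody data, the postpartum measurement will be used as the reference point". The value comes from Visit 5, failing that from the last available postpartum sample, and otherwise it is missing. SAP 9.2.3 builds on this: "The fold difference increase from postpartum value, i.e., the minimum significant ratio (MSR) determined during assay validation, will be reported". Its next sentence describes the MSR as the titer difference that exceeds assay variation. The outputs are introduced with "The following summaries, figures and listings will be produced using the MSR and will be presented using the SS", without saying how the MSR enters each one.

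The planned ADA tables are sample status by visit, titer statistics by time point, and a third described as "Summary of titer classification for all study participants who test positive at any visit will be presented by category". For that third table, SAP 9.2.2 says that a woman's "highest titer will be used to categorize" her, whenever it occurred. Individual titer plots, CZP/ADA plots per participant and a full listing are also planned. On the assay, SAP 9.2.1 says: "Samples that are confirmed as positive in the confirmatory assay will be evaluated in a titration assay to quantify the ADA level".

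Protocol 9.2 defines the postpartum baseline for plasma concentrations only, and Protocol 9.3.2 leaves the ADA detail to the SAP. The SAP's choice is therefore not a breach of the protocol.

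**The concern.** Formation is a change forward in time, and the postpartum sample lies at the end of follow-up. A fold measured back from the end point is small when antibodies have formed and stayed, and large when they have waned. It answers whether the titer was higher in pregnancy than afterwards, which is a different question from whether antibodies formed or rose.

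The women have taken CZP for at least 12 weeks before enrolment (Protocol 5.1), so some may already be ADA positive at Visit 2. To report on formation, the tables would need to separate those women from women who become positive later, and to count those whose titer rises. If the tables do not, a secondary objective rests on readers classifying women by hand from listings, without agreed rules for missing or inconclusive samples.

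**Working it through.** The plan gives no figure to reproduce. All titers and MSR values below are assumptions chosen to show how the outputs behave; they are not estimates of frequency.

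**1. What the fold shows.** Fold versus postpartum = titer at a pregnancy visit / postpartum titer. Fold versus Visit 2 = later titer / Visit 2 titer. A negative sample has no titer (SAP 9.2.1), so a ratio that needs one does not exist.

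| Visit 2, T2, T3, postpartum | Largest pregnancy fold vs postpartum | Largest later fold vs Visit 2 |
|---|---|---|
| 32, 64, 256, 512 (rising) | 256/512 = 0.5 | 512/32 = 16 |
| 512, 256, 64, 32 (falling) | 512/32 = 16 | 256/512 = 0.5 |
| neg, 64, 256, 256 (formed, persists) | 256/256 = 1 | none: newly positive |
| neg, 256, 128, 32 (formed, wanes) | 256/32 = 8 | none: newly positive |
| neg, 128, 64, neg (transient) | none | none: newly positive |
| 64, 64, 64, 64 (stable) | 1 | 1 |
| 32, 128, 512, 32 (transient boost) | 512/32 = 16 | 512/32 = 16 |

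Against postpartum, a steady decline and a transient boost both give 16, and persistent new formation and a stable titer both give 1. A transient or waning rise is still visible. The postpartum fold exists in 6 of the 7 paths and the Visit 2 fold in 4. Changing the reference alone is therefore not enough, and a newly positive category is needed.

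**2. Whether the planned tables separate the courses.** Take two sets of three women in one dosing regimen, each woman ADA positive at Visit 2 and at one later visit.

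- Set 1: 32 to 128, 128 to 512, 512 to 32. Folds later/Visit 2: 4, 4, 0.0625.
- Set 2: 32 to 512, 128 to 32, 512 to 128. Folds later/Visit 2: 16, 0.25, 0.25.

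In both sets, the titers at each visit are 32, 128 and 512, so the three tables coincide:

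- Status: 3 of 3 positive at each visit.
- Titer statistics at each visit: mean 672/3 = 224, minimum 32, maximum 512, geometric mean (2^21)^(1/3) = 128. The small-n rule in SAP 3.1 may suppress some of these, but equally in both sets.
- Titer class: highest titers are 128, 512 and 512, so 1 woman in >32 to ≤128 and 2 in >128 to ≤512.

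The number boosted at least MSR-fold nevertheless differs: 2 versus 1 for an MSR of 2 or 4, and 0 versus 1 for an MSR of 8. If the later visit is postpartum, the Visit 2/postpartum folds are 0.25, 0.25, 16 in Set 1 and 0.0625, 4, 4 in Set 2. Every fold above 1 belongs to a woman whose titer fell.

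**3. What can be recovered.** Newly positive = ever positive (the sum of the titer-class counts) − positive at Visit 2. This holds when every Visit 2 result is positive or negative. If a Visit 2 result is missing or inconclusive and the woman is later positive, the subtraction counts her as newly positive although her enrolment status is unknown. No such subtraction yields the boosted count.

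**The case against.** The postpartum reference has a design reason. At 12 weeks after delivery the mother's physiology is taken to be back to its state before pregnancy, each woman is her own control, and ADA are also used to interpret CZP exposure (Protocol 4.1, 4.2, 8.9.1). One reference for PK, covariates and ADA is coherent. The ADA variable is levels over the study, which the planned outputs do deliver, and SAP 9.2.3 never calls the fold formation. With about 20 women enrolled (Protocol 9.8), a reader can trace each course from the plots and listing. Visit 2 has limits of its own: it may be as late as 10 weeks' gestation.

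Much of this stands. It supports keeping the postpartum fold, and it means that no planned output is shown to be wrong. SAP 3.3 also already covers a missing postpartum sample, including after a spontaneous abortion, when none is taken (Protocol 7.2). The absent MSR value is only missing detail, since SAP 9.2.3 places it in the assay validation.

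The mismatch with the stated objective remains. The only ADA change measure in the plan runs against the direction of formation, and individual displays do not replace a count made under rules set in advance.

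**Conclusion.** The point holds as a cheap improvement. The fold referenced to postpartum does not measure ADA formation or boosting, and it does not exist when the postpartum sample is ADA negative. No planned table separates ADA present at enrolment from ADA newly formed or boosted. The boosted count cannot in general be derived from the tables, and the newly positive count can be obtained only by subtraction with complete, conclusive Visit 2 results. How many women this affects cannot be derived from the documents.

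A reader might infer three stronger things, and the documents support none of them:

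- That the ADA results as a whole are compromised. The status-by-visit table, titer summaries, plots and listings do not depend on the reference and remain valid.
- That women will be misclassified by a flag based on the postpartum fold. SAP 9.2.3 defines no such flag, and its wording on using the MSR does not fix the effect on any one output.
- That information is lost. Visit 2 is marked for ADA sampling in the Schedule of Activities, and individual results are listed.

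**What to change.** In SAP 3.3 and 9.2.3, name Visit 2 as the reference for ADA formation and add one descriptive table on the Safety Set. Evaluable means ADA positive or ADA negative under SAP 9.2.1. The categories are:

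1. Negative at Visit 2 and at all later evaluable samples, with at least one such sample.
2. Newly positive after a negative Visit 2 sample, by trimester or postpartum of the first positive.
3. Positive at Visit 2 with a later titer at least MSR-fold higher.
4. Positive at Visit 2 with a later evaluable sample and no such rise.
5. Not classifiable: Visit 2 missing or inconclusive, or no evaluable sample afterwards.

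Show the number classifiable as the denominator. If, say, 5 of 20 women were not classifiable and 3 were newly positive, counting the 5 as negative gives 3/20 = 15.0%, and setting them apart gives 3/15 = 20.0%.

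Keep the postpartum fold as a labelled secondary display, reported as not calculable when the postpartum sample is ADA negative. In SAP 9.2.3, separate the observed fold from the MSR, which is the assay threshold. Add a footnote that Visit 2 follows at least 12 weeks of CZP and may be as late as 10 weeks' gestation (Protocol 5.1), so the table describes formation or boosting after enrolment, not since first exposure or conception.

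The cost is SAP wording and one table, with no new sampling. The downside is small counts. Zero newly positive women would have an exact 95% upper limit of 1 − 0.025^(1/20) = 16.8% with 20 classifiable and 1 − 0.025^(1/15) = 21.8% with 15.

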3.4 Protocol deviations

No protocol deviation is permitted, either in retrospect or prospect.

Important protocol deviations are deviations from the protocol which potentially could have a meaningful impact on study conduct or on the key safety or PK outcomes (if applicable) for an individual study participant. The criteria for identifying important protocol deviations will be defined within the important protocol deviations document. Important protocol deviations will be reviewed as part of the ongoing data cleaning process and data evaluation. All important deviations will be identified and documented prior to database lock to confirm exclusion from analysis sets.

3.5 Analysis sets

There will be 4 analysis sets for the study: the All Study Participants Set (ASPS), the Enrolled Set (ES), the Safety Set (SS) and the Pharmacokinetic Per Protocol Set (PK-PPS).

3.5.1 All Study Participants Set

This will be the largest analysis set, consisting of all study participants who have signed the Informed Consent Form (ICF) and will include all participants who pass screening as well as screen failures. For participants who fail screening and subsequently re-screen, only the successful screening record(s) will be included in the ASPS.

3.5.2 Enrolled Set

The ES will include all study participants who are confirmed as having signed the ICF to participate in the study and have provided the first blood sample. For participants who re-enroll

after discontinuation, both enrollments will be included, and tables and listings will provide the participant identifiers in a footnote.

